### Procedures for Investigator to Withdraw Subjects

A subject will be withdrawn from the study if the subject requests to be withdrawn for any reason, if the subject does not follow study protocol regarding administration of the blinded intervention, if the subject is unable to continue due to deteriorating clinical status (related to COVID-19 or otherwise), or if the study is prematurely ended for any reason. The patient will continue with routine care per primary physician otherwise.

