### Primary and Secondary Study Endpoints:

The primary endpoint of this study is a Brief Smell Identification Test, a standardized and validated objective measure of olfactory function, administered 6 weeks from symptom onset.

The secondary endpoints of this study include patient-reported outcome measure surveys, a modified Brief Questionnaire of Olfactory Dysfunction - Negative Statements (QOD-NS) survey and Sino-Nasal Outcome Test (SNOT-22), administered at time points of 1, 2, 4, and 6 weeks after symptom onset.

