### Description of Procedures Being Performed

Patients will be recruited (utilizing inclusion and exclusion criteria outlined above) through the Otolaryngology Faculty Practices as well as the web based application STOP COVID NYC. Current recruitment goals are one hundred seventy six patients, with eighty eight patients in each group. After recruitment the patients will be block-randomized by a computer-generated sequence in a 1:1 allocation to treatment or control arms. Patients randomized to the treatment group will be allocated a supply of 1000 mg capsules of omega-3 fatty acid blend including 683 mg Eicosapentaenoic Acid and 252 mg Docosahexaenoic Acid) to be taken daily for 6 weeks. Patients randomized to the control group will receive a placebo and will follow the same regimen as the treatment group. Collection of data (described below) will occur through the use of the EPIC electronic medical record system, through phone conversations between investigators and subjects, and through information collected during office visits. The primary outcome studied will be the Brief Smell Identification Test (BSIT) which will be administered 6 weeks after symptom onset. The secondary outcomes include patient-reported outcome measure surveys, a modified Brief Questionnaire of Olfactory Dysfunction - Negative Statements (QOD-NS) survey and Sino-Nasal Outcome Test (SNOT-22), administered at time points of 1, 2, 4, and 6 weeks after symptom onset. After the conclusion of data collection a statistical analysis will be conducted to compare outcomes in the treatment and placebo arms.

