### Description of Data that Will Be Collected Included Long-term Follow-Up

Patient identifying information (which will be then de-identified and exchanged with a Subject ID), demographics, history of present illness, past medical history, past surgical history, medication list, medication allergies, Brief Smell Identification Test (BSIT) score, modified Brief Questionnaire of Olfactory Dysfunction - Negative Statements (QOD-NS) Score, and Sino-Nasal Outcome Test (SNOT-22) score. Patients will be followed for a period of six (6) weeks with repeat collections of interval patient history as well as QOD-NS and SNOT-22 survey scores at the one, two, four, and six week follow-up periods.

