## **Data**

### Description of Health Information that Will Be Viewed, Recorded, Or Generated

1. Data at the initial visit will include:
2. Documentation that patient meets all inclusion criteria and no exclusion criteria
3. Patient Identifying information (DOB, Name, MRN) and a Subject ID will be assigned
4. Patient's home address will be obtained in order to send BSIT kit and placebo or supplement.
5. Demographic information including age, gender, race and ethnicity
6. Patient history - history of present illness (including presence of symptoms, onset and duration of symptoms, associated symptoms, past medical history, past surgical history)
7. Past medical history
8. Past surgical history
9. List of medications and medication allergies
10. Brief Questionnaire of Olfactory Dysfunction - Negative Statements (QOD-NS) Score
11. Sino-Nasal Outcome Test (SNOT-22) Score
12. Follow-up visits at 1 week, 2 weeks and 4 weeks:
13. Patient interval history
14. Brief Questionnaire of Olfactory Dysfunction - Negative Statements (QOD-NS) Score
15. Sino-Nasal Outcome Test (SNOT-22) Score
16. Follow-up visit at 6 weeks:
17. Patient interval history
18. Brief Smell Identification Test (BSIT) Score
19. Brief Questionnaire of Olfactory Dysfunction - Negative Statements (QOD-NS) Score

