## 20. Sino-Nasal Outcome Test (SNOT-22) Score

Follow-up visits at 1 week, 2 weeks and 4 weeks:

1. Patient interval history
2. Brief Questionnaire of Olfactory Dysfunction - Negative Statements (QOD-NS) Score
3. Sino-Nasal Outcome Test (SNOT-22) Score

Follow-up visit at 6 weeks:

1. Patient interval history
2. Brief Smell Identification Test (BSIT) Score
3. Brief Questionnaire of Olfactory Dysfunction - Negative Statements (QOD-NS) Score
4. Sino-Nasal Outcome Test (SNOT-22) Score

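### Patients who do not follow administration of the blinded product are withdrawn from the study itself, with no week-6 BSIT provided, so the primary comparison loses a group selected after randomisation

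*Protocol*

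**What the plan says.** Under Procedures for Investigator to Withdraw Subjects, the protocol withdraws a subject from the study for several reasons. One of them is "if the subject does not follow study protocol regarding administration of the blinded intervention". For what follows it says only: "The patient will continue with routine care per primary physician otherwise".

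The primary endpoint is the BSIT, described under Primary and Secondary Study Endpoints as "a standardized and validated objective measure of olfactory function, administered 6 weeks from symptom onset". The visit lists in the Data section show "Brief Smell Identification Test (BSIT) Score" at the 6-week visit only. It is not listed at the initial visit or at weeks 1, 2 and 4. What is repeated during follow-up is "repeat collections of interval patient history as well as QOD-NS and SNOT-22 survey scores at the one, two, four, and six week follow-up periods".

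The analysis is announced under Description of Procedures Being Performed: "After the conclusion of data collection a statistical analysis will be conducted to compare outcomes in the treatment and placebo arms".

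A different rule stands under Provisions for Research Related Harm/Injury. A significant adverse reaction ends treatment at once; leaving the study is not mentioned there.

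**The concern.** Not following the product is something that happens after randomisation, and it may be related both to the arm and to how the sense of smell is recovering. A rule that ends study participation for it removes the primary outcome of those patients. The arms as compared are then no longer the arms as randomised.

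This is a matter of data collection, so it is not something to leave to an SAP. An analysis plan can define analysis sets and methods for missing values, but it cannot obtain a week-6 score from a patient who has left. With no BSIT at any earlier visit, there is not even a previous value of the same measure to lean on.

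**Working it through.** **Step 1: the passages side by side.**
- Withdrawal for not following administration is from the study, and only routine care is named afterwards.
- The six-week follow-up section is general and does not say that follow-up continues after withdrawal.
- The BSIT is listed once, at week 6.
- The rule for significant adverse reactions stops treatment only. It does not cover other non-adherence, such as doses missed for mild intolerance, and does not expressly provide a later BSIT.

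A patient withdrawn for non-adherence before week 6 therefore has no planned primary outcome.

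**Step 2: the plan's own figures.** The recruitment goal is 88 per arm, 2 × 88 = 176. The protocol gives no power, effect size, SD or dropout rate, so 88 cannot be reproduced and is not disputed. Everything below is illustration.

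**Step 3: worst-case bound.** Inputs are 12 items (Risks to Subjects) and 88 per arm, assuming a score of 0 to 12. One missing score can move an arm mean by at most 12/88 = 0.136 points. Four missing in one arm (4/88, about 5%) widen the range of possible arm differences by 4 × 12/88 = 0.55 points. Nine (about 10%) widen it by 9 × 12/88 = 1.23 points. These are extremes, not expectations.

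**Step 4: shift with no true effect.** Assumed: 45% recovered in each arm; BSIT mean 10.5 (SD 1.2) if recovered and 6.5 (SD 2) if not; 5% removal unless stated. The difference between outcome groups is 10.5 − 6.5 = 4 points. With removal rates a (recovered) and b (not recovered), the recovered share among retained patients is

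p = 0.45(1 − a) / [0.45(1 − a) + 0.55(1 − b)],

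and the shift is 4 × (p − 0.45), because equal 5% removal leaves the control share at 0.45. The last column comes from a simulation of 40,000 trials per row, with a pooled t-test on retained patients and scores capped to 0–12. The cap makes its shifts slightly smaller.

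| Omega-3 arm: a, b | p | Shift by formula | Simulated shift; SE; type I error |
|---|---|---|---|
| 10%, 5% | 0.4050/0.9275 = 0.437 | −0.053 | −0.05; 0.399; 5.2% |
| 20%, 5% | 0.3600/0.8825 = 0.408 | −0.168 | −0.16; 0.404; 6.9% |
| 5%, 10% | 0.4275/0.9225 = 0.463 | +0.054 | +0.05; 0.399; 5.2% |
| 5%, 20% | 0.4275/0.8675 = 0.493 | +0.171 | +0.17; 0.404; 7.2% |

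The larger shift is about 0.17/0.404 = 0.4 standard errors. Its sign depends on which outcome group is removed.

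**Step 5: when nothing is shifted.** If 10% or 20% of the omega-3 arm is removed regardless of outcome, the simulated shift is 0.00 (type I error 5.1% and 5.0%). If recovered patients are removed at 10% or 20% in both arms alike, it is again 0.00 (4.8% and 5.1%).

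**Step 6: with an assumed true effect.** For recovery of 65% v 45%, complete follow-up gives an estimate of 0.79 points. Removing 20% of recovered omega-3 patients gives 0.63; removing 20% of non-recovered ones gives 0.94. Removed patients are assumed to have had the full benefit.

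**The case against.** The best reply has four parts.

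- **The protocol already has a treatment-only stop.** Significant adverse reactions end treatment, not participation, and side effects are the most obvious arm-related reason to stop omega-3. This narrows the route to unequal removal. It does not close it, because milder intolerance and plain non-adherence still fall under the withdrawal rule.
- **Partial checks are possible.** A reader might infer that the trial could not tell whether withdrawal had distorted the result. That goes too far. Withdrawals can be counted by arm, and the QOD-NS and SNOT-22 scores taken before withdrawal can be compared between withdrawn and retained patients and used in sensitivity analyses. This assumes those scores are kept: the deletion rule stands under patient-requested withdrawal and is not said to cover withdrawal by the investigator. Only the missing BSIT itself is beyond recovery.
- **The illustrated harm is small and rests on assumptions.** Several scenarios give no shift, and 10% selective removal barely moves the type I error. The protocol also calls the side effects of omega-3 typically mild. This stands: the case rests on following all randomised patients, not on a demonstrated distortion.
- **Keeping non-adherent patients may dilute the effect.** This also stands. The figures in the last step of the working do not allow for it.

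**Conclusion.** The point holds and should be fixed. Followed as written, the withdrawal rule leaves some randomised patients without the primary outcome and omits them from the comparison of arms, and no later analysis can restore the value.

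How many patients this affects, and the direction and size of any bias, are unknown. Bias under no true effect needs removal that both depends on outcome and differs by arm. Under the assumed values it is about 0.05 points at 10% selective removal in one arm (type I error about 5%) and about 0.17 points at 20% (about 7%).

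Two stronger readings are tempting and not supported. One is that the trial's result will be biased, or its type I error inflated: the protocol gives no rate or pattern of withdrawal from which to say so. The other is that the protocol forbids a BSIT after withdrawal: no sentence does, but none calls for one either.

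**What to change.** Under Procedures for Investigator to Withdraw Subjects, separate stopping product from leaving the study, consistently with the treatment-only wording under Provisions for Research Related Harm/Injury. For example:

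> A patient who does not follow administration of the blinded product, or stops it, and still consents remains in follow-up. Surveys and adverse-event checks continue as scheduled, and the week-6 BSIT is completed where the patient is able. The patient is kept in the randomised arm for the main comparison. Only withdrawal of consent ends data collection for a patient.

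The clinical reasons for stopping product stay as they are.

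The cost is protocol and consent wording and a few more contacts, with no extra patients. The means are already in place: the patient's "home address will be obtained in order to send BSIT kit and placebo or supplement", and data are already collected "through phone conversations between investigators and subjects". The main comparison then estimates the effect of being assigned omega-3, which non-adherence may dilute. An analysis of adherent patients can be added as supplementary.

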#### Exclusion Criteria

- Patients  $< 18$  years of age
- Patients who are unable to provide informed consent
- Patients without a positive COVID-19 PCR result obtained through nasopharyngeal swab
- Patients with a COVID-19 diagnosis but without self-reported anosmia
- Patients with severe COVID-19 disease as defined by the Mount Sinai Health System Treatment Guidelines for SARS-COV-2 (requiring high flow nasal cannula, non-rebreather, CPAP/BIPAP, or mechanical ventilation OR patients requiring pressor medication OR patients with evidence of end organ damage)
- Patients with pre-existing self-reported olfactory dysfunction
- Patients with a history of chronic nasal/sinus infections (rhinosinusitis) or history of endoscopic sinus surgery
- Patients using nasal steroid sprays or irrigations for any reason
- Patients who are prisoners of the state
- Patients who have psychiatric or developmental disorder conditions that may impair ability to provide informed consent

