#### Safeguard to protect Subjects' rights and welfare

The principal and co-investigators will maintain communication with the subjects in order to help identify any issues that arise. The PI, co-investigator, or a delegate will inquire about adverse events throughout the study via phone calls and in-office visits. The PI will maintain records of all adverse events and will use the NCI Common Terminology Criteria for Adverse Events (CTCAE) for documentation. Adverse events occurring during the study will be reported to the Mount Sinai Program for the Protection of Human Subjects (PPHS). Any suspension of the study will be reported to the PI and the IRB. Additionally, a data and safety monitoring committee (DSMC) will be established and consist of the principal investigator and co-investigators. Adverse events will be reviewed every three months.

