### **Safety Monitoring:**

Patients will be asked to report adverse effects related to omega-3 use. Minor side effects are not uncommon, and typically include gastrointestinal distress or fishy test. Serious adverse events are exceedingly rare. Patients will be instructed to report any potential adverse events to the PI which will be recorded. Patients will be screened for adverse events at each of the data collection check-points (1 week, 2 weeks, 4 weeks, and 6 weeks).

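### Subjects who cannot continue because they deteriorate are withdrawn from the whole study, so their safety outcome and week 6 assessments need not be collected

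*Protocol*

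**What the plan says.** The Protocol section *Procedures for Investigator to Withdraw Subjects* begins "A subject will be withdrawn from the study" and lists the grounds. One of them is "if the subject is unable to continue due to deteriorating clinical status (related to COVID-19 or otherwise". The only provision for what follows is "The patient will continue with routine care per primary physician otherwise".

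Safety collection is set out in three other sections:

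- *Safeguard to protect Subjects' rights and welfare*: the investigators or a delegate "will inquire about adverse events throughout the study via phone calls and in-office visits", and "The PI will maintain records of all adverse events". These events are reviewed every three months.
- *Description of Data that Will Be Collected Included Long-term Follow-Up*: "Patients will be followed for a period of six (6) weeks with repeat collections of interval patient history".
- *Safety Monitoring*: "Patients will be screened for adverse events at each of the data collection check-points (1 week, 2 weeks, 4 weeks, and 6 weeks".

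Three further provisions bear on the point. *Provisions for Research Related Harm/Injury* stops the treatment, and only the treatment, after a significant adverse reaction to it. *Procedures for Subjects to Request Withdrawal* has a sentence deleting all stored information when a patient withdraws. *Exclusion Criteria* keeps out "Patients with severe COVID-19 disease as defined by the Mount Sinai Health System Treatment Guidelines for SARS-COV-2".

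**The concern.** Stopping a product and leaving a study are different things, and the withdrawal section treats them as one for subjects who deteriorate. The reason for leaving is a clinical event after randomisation, so follow-up is lost selectively, in the subjects who do worst.

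Two kinds of data are at stake. One is the safety record: the three-monthly review could see an event at its grade on withdrawal and never learn that it later worsened or was fatal before week 6. The other is efficacy: the Brief Smell Identification Test (BSIT) is given at 6 weeks, so any subject withdrawn earlier has no primary outcome, and the QOD-NS and SNOT-22 surveys still due are missing as well.

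This is a matter of trial conduct that the protocol fixes. A statistical analysis plan can say how missing data are handled, but it cannot recover data that the protocol did not require anyone to collect.

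**Working it through.** The protocol states no figure on this point, so there is none to reproduce. The check is a reading of the sections together, followed by simple arithmetic on the visit schedule.

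**Step 1: what the subject leaves.** The withdrawal section says the study. The harm and injury section shows that the protocol can write a treatment-only stop when it means one. That stop covers significant reactions to the treatment. It does not cover worsening COVID-19 or another illness not attributed to the capsules.

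**Step 2: whether safety collection continues.** Each of the three safety provisions is a study activity:

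| Section | Activity | Extended to withdrawn subjects? |
|---|---|---|
| *Safeguard to protect Subjects' rights and welfare* | Inquiry about adverse events over the course of the study | Not stated |
| *Description of Data...* | Six weeks of follow-up with interval history and surveys | Not stated |
| *Safety Monitoring* | Screening at weeks 1, 2, 4 and 6 | Not stated |

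None forbids later contact. None requires it either, and the one stated sequel to withdrawal is routine care.

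**Step 3: what is kept and what can be lost.** An event that occurs before withdrawal falls under the duty to record all adverse events, so the trigger should be captured. What need not be captured comes afterwards: resolution or worsening of that event, a new serious event, or a death up to week 6. The week 6 BSIT and any surveys still due go as well.

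**Step 4: the gap per subject.** Inputs: follow-up of 6 weeks and check-points at weeks 1, 2, 4 and 6. For withdrawal just after the check-point at week *w*, the weeks without required contact are 6 − *w*, and the missed check-points are those later than *w*.

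- After week 1: 6 − 1 = 5 weeks; weeks 2, 4 and 6 missed (3 of 4).
- After week 2: 6 − 2 = 4 weeks; weeks 4 and 6 missed (2 of 4).
- After week 4: 6 − 4 = 2 weeks; week 6 missed (1 of 4).

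These week counts are maxima, since withdrawal later in an interval leaves a shorter gap. In addition, *Primary and Secondary Study Endpoints* counts the survey times from symptom onset, so a subject enrolled after week 1 or 2 never had all four contacts to lose.

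**Step 5: who is likely to be affected.** Severe COVID-19 is excluded at entry. That may keep the number low. It also means that any progression to severe disease happens after entry, in the subjects this rule is likely to remove. The protocol gives no rate of deterioration, so no count can be derived.

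**The case against.** The best defence is that the gap is one of silence. The safety sections speak of patients in general, with no exception for those withdrawn, and inquiry over the course of the study could mean the trial period rather than the individual's participation. That reading is possible, but the withdrawal rule itself is not silent: it takes the subject out of the study and hands over to routine care. A team that stops there has followed the text.

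A second defence is the treatment-only stop for significant reactions to treatment. It narrows the problem without closing it, because deterioration for other reasons stays under the withdrawal rule, and attribution under blinding is imperfect.

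A third is that a subject unable to continue can give no more data. Being unable to take capsules or complete a smell test does not prevent a chart check or a phone call.

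Some stronger readings are tempting, and the document does not support them:

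- *Safety follow-up is forbidden after withdrawal.* No section says so; it is only not required.
- *Everyone who worsens is removed.* The rule reaches only those unable to continue.
- *The serious event itself goes unrecorded.* It should be on record before withdrawal. Progression to severe COVID-19 would usually already count as serious, so a later worsening in the same subject would not change the number of subjects with a serious event. What is lost is the later grade or the death.
- *The subject's earlier data are erased.* The deletion sentence stands under withdrawal at the subject's request. Applying it to withdrawal by the investigator is an inference, although its general wording leaves room for doubt.

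It would be equally wrong to say that the harm stops at the safety record, since the week 6 BSIT and later surveys go with it.

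**Conclusion.** The point holds as a defect in what the withdrawal section fixes. Deterioration that prevents a subject from continuing ends study participation, and nothing obliges the team to learn the subject's outcome to week 6 or to collect the remaining efficacy measures.

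The conclusion assumes that withdrawal from the study means what it says, and that duties not extended to withdrawn subjects do not bind the team. The per-subject loss is bounded by the schedule, but the number of subjects is unknown and may be small or zero; the protocol describes serious events with omega-3 as very rare. No effect on the treatment comparison can be quantified from the document. The change is worth making because the loss is selective and the remedy cheap, not because a large distortion has been shown.

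**What to change.** Amend *Procedures for Investigator to Withdraw Subjects* as follows:

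1. Deterioration ends only the product, or the procedures the subject cannot continue, and not study participation.
2. For every randomised subject who has not withdrawn consent, ascertain vital status, serious adverse events and the outcome of ongoing events to week 6. Use the EPIC record, already the named data source, or the phone contacts already planned.
3. Collect the week 6 BSIT and the remaining QOD-NS and SNOT-22 surveys where feasible.
4. Report these results by randomised arm.
5. State that the deletion sentence under *Procedures for Subjects to Request Withdrawal* does not apply when the investigator withdraws a subject.

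The cost is a short amendment and, for each such subject, a chart check or call by existing staff with a little extra data entry. Care received outside the health system will be captured incompletely.
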